The University of Kentucky Chandler Hospital is a large level-1 Trauma center in eastern Kentucky. The Orthopedics Department has locations within the Kentucky clinic that serve as a dedicated research space, which contain computers with access to password-protected research drives.

The Principle Investigator (PI) will be responsible for overseeing the study and ensuring consistency throughout the project. The orthopedic PI will serve as the research coordinator and assist in data collection and analysis. Recruitment and consent will be performed by the PI or the research assistant. Each member of the research staff has passed the CITI exam on ethical conduct of research and have received training and supervision regarding patient confidentiality and study protocol. The PI will meet with all research staff periodically to review each role and ensure adequate training for the respective positions. Upon enrollment of each patient, the corresponding surgical team will be counseled concerning the details of the study and their role, prior to admitting the patient into the OR.

The PI and research assistant will be responsible for institutional /IRB communication as well as data review and assistance with follow-up patient coordination as needed. There are no anticipated adverse consequences associated with this study, however, the principal investigator and research assistant will both be available should any unexpected medical or psychological problems arise. The research subjects will be provided with appropriate contact information in the consent form and will be provided with the PIs contact information at the time of enrollment as well.

21. Recruitment Methods

No formal external recruitment methods will be used for this study, as acute trauma patients that are moderately to severely injured are universally admitted to the hospital after injury while awaiting surgery. Patients will be identified, screened, and approached for enrollment in the study as noted above (see 8. Study Timeline). After review and screening, the patient will be given the opportunity to ask researchers questions about the study. There will be no financial compensation in return for participation in this study.

22. Confidentiality

As part of our design, researchers will have access to patients' names and phone numbers in order to collect the required data. Upon enrollment, each patient will also be assigned a unique identifier. All patient personal information will be stored in a master list that links the patient's identifying information to their medical record number, which will be maintained in a separate, locked file that only approved research personnel will have access to. During the data collection period, researchers will not directly use this master list and, instead, will draw upon information from a separate that contains only the patient's first name, phone number, and unique patient identifier

All paper data collection documents are kept in locked file cabinets within locked offices that are accessible only to the project investigators and staff. All online databases are password protected to guard against unauthorized access and only approved research personnel will be granted access.

23. Provisions to Protect the Privacy Interests of Subjects (HIPAA)

All eligible subjects will be identified by orthopedic trauma team and researchers during morning fracture conference or upon presentation to the ED. After this point, only approved research personnel will have access to patients' private health information. All research will be stored electronically on secure research drives or locked offices as described above.

Only health information related to their orthopedic injury and surgery will be reviewed for the purposes of this study. Other unrelated personal health information will not be accessed or used in any way. All subjects will sign a HIPAA authorization form for use of any protected health information to be used for research purposes, as stated above.

24. Compensation for Research-Related Injury

There will be no additional compensation for research related injury as all treatments/medications are approved for postoperative pain management. Patients would be treated for any complications of surgery including non-union or fractures that may be slow to heal using approved methods by their treating surgeon consistent with standard of care. The patient would be responsible for all costs associated with this treatment.

25. Economic Burden to Subjects

Although ketorolac is part of the routine trauma acute pain protocol, the cost of the study medication (ketorolac) will be paid for by either an internal or external grant. All other treatment costs are within the standard of care and the expenses will be paid for by the patient and their health insurance. There is no additional post-operative follow-up required for this study beyond the surgeon's standard follow-up routine. There will be no financial compensation in return for participation in this study. The cost to analyze and collect the specimens for analysis will also be covered by the internal or external grant.

26. Consent Process

Consent and/or Authorization by a Legally Authorized Representative (LAR)

Eligible patients will be approached for their consent to participate. Informed consent will be obtained prior to the collection of any study related data. To encourage a high level of participation from eligible patients, the attending surgeon may be involved in the consent conversation. The research coordinator and surgeon may initiate the conversation together.

By virtue of the types of injuries studied (resulting from high energy mechanisms such as high-speed motor vehicle crashes, high falls, and blast injuries) it is expected that a large proportion (> 30%) to have an associated traumatic brain injury which may render them unable to provide consent for the study. It will be important not to exclude these patients from the study, as it would significantly reduce our ability to produce generalizable knowledge. These patients are at no greater risk of adverse consequences by virtue of their participation in the study and should be given the same opportunity to participate.

Consistent with Kentucky health care decision statutes for choosing a legally authorized representative for adult subjects unable to consent, one of the following responsible parties, in the following order of priority (if no individual in a prior class is reasonably available, willing, and competent to act), is authorized to make research participation decisions on behalf of the person: (a) the judicially-appointed guardian of the person, if the guardian has been appointed and if the decisions to be made under the consent are within the scope of the guardianship; (b) the attorney-in-fact named in a durable power of attorney, if the durable power of attorney specifically includes authority for the decisions to be made under the consent; (c) the spouse of the person; (d) an adult child of the person, or if the person has more than one (1) child, the majority of the adult children who are reasonably available for consultation; (e) the parents of the subject; (f) the nearest living relative, or if more than one of the same relation, a majority of the nearest living relatives.

Consent by a legally authorized representative should involve all the same considerations that informed consent from a competent subject involves.

Guidance will be provided to assist the LAR in making the consent decision. They will be advised to base the decision on the participant's expressed wishes, or, if these are not known, what they believe the participant would have desired under the circumstances of the injury, their beliefs and values. If the LAR does not know what the participant would have wanted, the LAR will be advised to base the decision with the participant's best interest in mind. They will be asked to carefully consider how much leeway the participant would likely give the LAR in making the choice about participation in the study.

Recognizing that consent is an ongoing process, the study team will encourage the participants to ask additional questions that may arise during their participation in the study.

27. Process to Document Consent in Writing

The consent will be documented in accordance with the guidelines set forth by the IRB and ORI at UK. The patient will receive a copy of this consent for their personal records during the enrollment process.

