Monitoring of the progress of clinical investigations and the safety of participants: The proposed medication for this investigation is a commonly utilized substance for pain control. Patients will be monitored for adverse effects of these medications continuously while they are an inpatient. Please refer to Study Drug information and Informed Consent Appendix B for further details. The research team will work closely with the medical management team daily to note if any of these difficulties should arise. Other minor side effects will be recorded and monitored through chart review (nausea, abdominal pain, minor bruising and bleeding) at the conclusion of the inpatient admission. If necessary, blinding will be broken if any potential side effects are noted and the information regarding treatment would be helpful to the treating team. The clinical medical monitor of the investigation will be obtained with the help of CCTS and that person will be added to the study personnel. The PI will be blinded to the subject treatment arm, and thus limit bias in reporting.

Compliance:

The research team will meet monthly to discuss and review any of the above recorded events and report adverse events to the IRB accordingly. A yearly report will be filed with the IRB with regards to overall data safety. Study suspension/termination: In the event that there is a noted increase in the serious side effects of taking the study drug, the study will be suspended for review.

Data Accuracy:

The research team will meet monthly to go over the collected data and perform spot reviews to determine the accuracy of the data collection from the medical record and study procedures.

[Back to Top](#)

Future Use and Sharing of Material (e.g., Data/Specimens/Information)

If the material collected for this study will be used by members of the research team or shared with other researchers for future studies, please address the following:

- list the biological specimens and/or information that will be kept
- briefly describe the types, categories and/or purposes of the future research
- describe any risks of the additional use
- describe privacy/confidentiality protections that will be put into place
- describe the period of time specimens/information may be used
- describe procedures for sharing specimens/information with secondary researchers
- describe the process for, and limitations to, withdrawal of specimens/data

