Interventional Model Description: Compare the effectiveness of a NSAID to placebo in acute trauma setting.

Masking: Triple (Participant, Care Provider, Investigator)

Masking Description: Participant medical team will be blinded to the treatment or placebo intervention.

3. Outcome Measures

Primary Outcome: Length of Hospital Stay

Secondary Outcomes:

- Daily Concentrations of IL-1, IL-6, IL-10, and PGE2
- Incidence of Post-Traumatic Complications (e.g., bacterial pneumonia, SIRS, MODS, ARDS, and AKI)
- Mortality
- Visual Analogue Pain Scores
- Inpatient Morphine Milligram Equivalents
- Change in Inpatient Subjective Pain Reports
- Change in Outpatient Subjective Pain Reports

4. Background

Accidental trauma is the 4th leading cause of death in the United States, and it is associated with a complex inflammatory response. This response is associated with post-traumatic complications such as multi-organ dysfunction syndrome (MODS), bacterial pneumonia, acute respiratory distress syndrome (ARDS), systemic inflammatory response syndrome (SIRS), and post traumatic pain (PTP). It is unknown whether early modulation of inflammatory cytokines is associated with improved patient outcomes, reduced narcotic requirements, and improved patient subjective pain after hospital discharge.

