Our preliminary data has shown: (1) elevated blood cytokine concentrations during the acute phase of trauma are correlated with the development of fatal post-traumatic complications, (2) that early administration of a non-steroidal anti-inflammatory drug (NSAID) resulted in decreased blood serum levels of IL-6, Prostaglandin E2 (PGE2), improved pulmonary edema, and enhanced arterioles ability to vasoconstrict in response to hemorrhage in animal models, and (3) that the addition of the internal physiologic parameters (inflammatory cytokines) to New Injury Severity Score (NISS – a marker of the external anatomical insult) significantly improves the ability to predict hospital length of stay of trauma patients when compared to NISS alone. Our group is the first to use an integrative approach that combines the external anatomic injury data with the internal physiologic response for accurate prediction of patient's clinical outcome. Therefore, if we apply this same mindset to treatment, we can improve the trauma patients' care by addressing both parameters as opposed to solely focusing on the external injury as done in the past. Our ability to modify post-traumatic physiologic response via short-term administration of a NSAID may lead to improved patient outcome.

Over the last decade, clinicians remain puzzled over the safety of NSAID administration after fracture in terms of bone union. In addition, given the current landscape for opioid epidemic in the United States, alternative non-opioid pain management during acute trauma has the potential to reduce opioid consumption and represents a pivotal component of multimodal analgesia strategy.

5. Inclusion and Exclusion Criteria

Inclusion Criteria

- Patient aged 18-75
 - a. Patient or legally authorized representative (LAR) able to provide consent.
 - b. Patient with New Injury Severity Score (NISS) > 9 at time of admission determined by trauma staff.
 - c. Anticipated admission \geq 5 days

Exclusion Criteria

- d. Patient age < 18 or > 75
- e. Patients with injury more than 24 hours prior to evaluation
- f. Hemorrhagic shock or risk of significant hemorrhage.
- g. Patients with preexisting inflammatory medical condition such as inflammatory arthropathy or inflammatory bowel disease
- h. Patients with acquired immunodeficiency syndrome (AIDS)
- i. Patients who are pregnant
- j. Patients with active GI bleed or ulceration

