- k. Patients with chronic use of steroids or immune modulating drugs or history of organ transplantation
- l. Patients with preexisting chronic renal, liver, or lung disease
- m. Patients with history of myocardial infarctions
- n. Patients with chronic heart failure
- o. Patients with allergy to NSAID
- p. Patients with coagulation defects (e.g., clotting factor deficiencies, thrombophilia, or any bleeding disorder)
- q. Patients receiving chronic opioid therapy or treatment for opioid use disorder.

6. Sample Size Calculation

Pretrial sample size calculations were performed regarding LOS because this will be the primary outcome measure of the clinical trial. Using a significance level of 0.05 and an assumed SD of 1.5 days, a sample size of 42 patients per group (84 total) would yield 80% power to detect a difference of 0.928 days in average LOS between the placebo and ketorolac groups. Allowing for a dropout rate up to 25%, the target enrollment will be 112 patients total, with 56 patients per group. Power calculations were performed using nQuery 8.5 (Statistical Solutions Ltd; Cork, Ireland).

7. Statistical Analysis Plan

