Patients with pre-existing medical co-morbidities and contraindications to ketorolac will be excluded from the study (see 5 for detailed exclusion criteria)

Patients in the treatment group will receive 15 mg IV ketorolac every 6 hours for 5 days after admission.

e. **Post-operative inpatient care:** Enrolled patients will have daily blood samples (10 cc) will be collected post-admission and at 24 hours intervals for 5 days by blinded health care personnel. The initial blood sample will be collected within 12 hours of initial injury and before the first scheduled administration of ketorolac to establish baseline cytokine profile. Subsequent blood sample collection will be 24 hours apart. Medication compliance and monitoring will be performed daily by the same research coordinators.

Sandwich ELISA will be used to determine the concentrations of IL-1, IL-6, IL-10, and PGE2 in obtained blood samples. Blinded quality control samples will be included in every batch for each ELISA assay. This will allow for the calculation of coefficient of variation (CV) within and across patient cohorts. In the present study, the CV will be calculated for IL-1, IL-6, IL-10, and PGE2. If wide variations are observed among the analytes during the analysis, we will restrict our analysis to analytes in which the CV is less than 20%.

In addition to the standard trauma labs (Sodium, Potassium, Creatinine, Lactic acid, Glucose, Platelet, blood urea nitrogen (BUN), hematocrit, and white blood cell count), patient demographics (sex, age, and BMI), injury data (mechanism of injury, NISS, and types of surgical/procedural interventions), posttraumatic complications (occurrence of bacterial pneumonia, ARDS, SIRS, MODS), complications defined in the National Trauma Dataset, and inflammatory data will be collected. This data will be maintained in our clinical database (REDCap) by a full-time Clinical Study Coordinator.

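### No by-arm comparison of bleeding is prespecified, although three exclusions screen for bleeding risk and bleeding events are already recorded

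*Combined protocol and SAP*

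**What the plan says.** **Outcomes.** Section 3 (Outcome Measures) makes length of stay primary. Its secondary outcomes are cytokines, mortality, pain and opioid measures, and "Incidence of Post-Traumatic Complications (e.g., bacterial pneumonia, SIRS, MODS, ARDS, and AKI". Bleeding, transfusion and hematocrit are not named.

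**Eligibility.** Section 5 excludes, under (f), "Hemorrhagic shock or risk of significant hemorrhage"; under (j), "Patients with active GI bleed or ulceration"; and under (p), "Patients with coagulation defects (e.g., clotting factor deficiencies, thrombophilia, or any bleeding disorder".

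**Capture.** The Data and Safety Monitoring text of the IRB application describes continuous inpatient monitoring for adverse effects and then adds: "Other minor side effects will be recorded and monitored through chart review (nausea, abdominal pain, minor bruising and bleeding". Protocol Section 13 sends medication effects and other medical complications to an adverse event log that is reviewed monthly. Section 10(e) also collects complications from the National Trauma Dataset, whose contents are not listed, and "standard trauma labs (Sodium, Potassium, Creatinine, Lactic acid, Glucose, Platelet, blood urea nitrogen (BUN), hematocrit, and white blood cell count".

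**Analysis.** Section 7 gives models for length of stay, VAS, MME and cytokines, and t-tests or Fisher tests for demographic and clinical variables. It does not mention adverse events, bleeding or hematocrit. The logistic regression in the Research Procedures text (Aim 1) is framed around predictor groups, the predictors of interest being inflammatory markers and NISS; treatment arm is not named as a term.

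**Statement already made.** The Continuation Review section reports interim results in 35 versus 35 patients. It concludes that no short-term adverse effects were apparent and that the results support using the drug.

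**The concern.** The plan takes bleeding seriously enough to screen for it three times at entry, and then sets no comparison of it after dosing. Events are collected, but they have no outcome definition, no denominator and no prespecified comparison by arm. A favourable safety sentence can therefore rest on an impression from a log. The reader of the trial report would not learn how large an excess of bleeding the data leave open. At this sample size that excess is not small, so a statement without an interval says more than the data can support. The primary result is not affected; what is at stake is the safety claim that will accompany it.

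**Working it through.** **1. The plan's own figure.** Section 6 uses a difference of 0.928 days, SD 1.5, alpha 0.05 and 80% power. A two-sided, two-sample t-test with 42 per group has power 0.800, so the figure reproduces. Dropout: 42 / (1 − 0.25) = 56 per group, 112 in total. The trial was sized for length of stay; no event rate entered the calculation.

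**2. Patients available.** The Continuation Review section gives 108 enrolled. Assuming an equal split, 108 / 2 = 54 per arm.

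**3. What zero events would show.** The one-sided 95% upper bound on a rate after 0 events in n patients is 1 − 0.05^(1/n).

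| n per arm | Upper bound |
|---|---|
| 35 (interim) | 8.2% |
| 54 (enrolled, equal split) | 5.4% |
| 56 (planned) | 5.2% |

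**4. What a test would show.** The documents give no bleeding rate, so the rates here are assumptions. Power is the sum, over all pairs of binomial counts, of the probability of each pair for which the two-sided Fisher p-value is below 0.05, with n = 54 per arm.

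| Placebo vs ketorolac | Power |
|---|---|
| 5% vs 10% | 7.3% |
| 5% vs 15% | 27.6% |
| 10% vs 20% | 21.3% |

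If the placebo arm had no events, 5 of 54 on ketorolac gives p = 0.057 and 6 of 54 gives p = 0.027. Six bleeds against none would be needed for significance. The analysis has to be estimation.

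**5. Whether hematocrit could do better.** With 54 per arm, a t-test has 80% power for a mean shift of 0.544 SD. For assumed SDs of 4, 5 and 6 points this is 2.18, 2.72 and 3.26 points. That is a shift in the mean of the whole arm. If bleeding is confined to some patients, the shift equals the excess rate times the drop per bleed. At 5% versus 15%, with an assumed drop of 6 to 12 points:

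- 0.10 × 6 = 0.6 points; 0.10 × 12 = 1.2 points
- simulated t-test power over SD 4 to 6: 8% to 21%, against 28% for Fisher

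At 5% versus 10% the simulated power is 6% to 9%, against 7%. A 3-point mean shift from a 10-percentage-point excess would need a drop of 3 / 0.10 = 30 points per bleed. Hematocrit is therefore no more sensitive than event counts unless the loss is spread across most patients, and the documents give no ground for assuming that.

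**The case against.** **The plan does not ignore bleeding, and could compare it.** The complications outcome is an open list, National Trauma Dataset complications are collected, and Section 7 has group tests for clinical variables. The monitoring text names bleeding among the other, minor effects; serious ones may be covered in the prescribing information, the consent appendix or the risk mitigation plan, none of which is shown. This stands against any claim that bleeding is uncollected or will never be compared. It does not supply a prespecified comparison, because no text shown names one.

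**An exclusion does not by itself require an outcome.** This is true: renal, liver, lung and cardiac disease are excluded too, and (p) also covers thrombophilia. The case rests on three bleeding-related exclusions together with a safety conclusion already drawn.

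**The interim statement is not part of the plan.** Also true, and the attached abstract is not shown, so what it compared is unknown. It does show that such a conclusion is likely to be drawn.

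**It is late.** The ORI screening comments record enrollment as closed, and by-arm interim results exist. The analysis cannot be presented as prespecified, but the estimate is still worth having.

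Three stronger readings are tempting and are not supported:

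- *Hematocrit would reveal an excess that event counts miss.* Step 5 of the working shows otherwise for bleeding in a minority of patients. The documents also give no sampling schedule for hematocrit and show no pre-dose value; the Section 9 schedule and the baseline sample in Section 10(e) concern the study blood draws for cytokines. Injury, surgery and transfusion affect hematocrit as well.
- *Transfusion can be added from data in hand.* The documents mention transfusion nowhere.
- *Exclusion (f) contradicts the enrollment of brain-injured patients, affecting about 0.30 × 54 = 16 on ketorolac.* The remark "These patients are at no greater risk of adverse consequences by virtue of their participation in the study" stands in Section 26, which concerns inability to consent. Exclusion (f) can still be applied to each such patient, and the expectation of more than 30% describes the injuries studied, not those enrolled after screening. This is an ambiguity and not a contradiction.

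**Conclusion.** The point holds as a gap in prespecification: Sections 3 and 7 contain no by-arm analysis of bleeding, although the plan treats bleeding as a hazard and records it. Its consequence is a safety statement with no bound. Even with no bleeds at all, 54 patients would leave a rate of up to 5.4% possible, and the interim 35 up to 8.2%. A hypothesis test would have little power, at 7% to 28% over the assumed rates, so an interval is the useful output. These figures assume an equal split of the 108 enrolled, and the power figures also rest on event rates the documents do not give. Because the point touches neither the primary outcome nor the sample size, it is an inexpensive improvement and not a flaw that undermines the trial.

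**What to change.** **Section 3.** Add a safety outcome: any recorded bleeding event after the first dose, of any severity, from the chart review and the adverse event log. State the window. If it runs to discharge, its length is itself the primary outcome and may differ by arm, so also give counts through Day 5 where event dates allow.

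**Section 7.** Report counts and denominators by arm and the risk difference with an exact 95% confidence interval. Describe this as estimation and not as a powered test. State that the safety conclusion will go no further than the interval supports.

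**Supportive data only.** Where dated values exist, summarise hematocrit and creatinine by arm. Do not base the safety conclusion on hematocrit.

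**Labelling.** State that the analysis was added after enrollment closed and after by-arm interim results had been reported.

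**Clarification.** Reconcile exclusion (f) with the consent text (Section 26 and the matching text in the IRB application) and with the statement on population risk in Section 28, so that it is clear to whom the safety statement applies.

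**Cost.** A paragraph in each of Sections 3 and 7, with no new patients and no new data collection. The downside is that the interval will be wide and the safety statement less favourable.
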